4.3.3. Post-baseline Analyses of Categorical Variables

Categorical variables will be compared between treatment groups using the Pearson chi-square test if the expected count is at least 5 in at least 80% of the cells; otherwise, Fisher's exact test will be used. Summaries for these variables will include the between-treatment p-value and the

descriptive statistics: number and proportion of patients. For post-baseline outcome variables, the relative risk estimate and the associated 95% CI will be provided, if there are at least 10 patients with the outcome.

If the categorical variable is associated with a scheduled post-baseline measurement, then a patient must have a measurement of the variable to be included. However, when the categorical variable is the occurrence of an event (yes/no), such as development of an adverse event (AE), then all randomized patients will be included in the analysis.

4.3.4. Time-to-Event Analyses

Time-to-event analyses will be performed for each of the adjudicated outcomes. For each analysis, all adjudicated events in the locked database will be used.

Time-to-event variables will be analyzed using survival analysis methodology if the total number of outcomes is 10 or more. A Cox proportional hazards regression analysis, where the model only includes a fixed effect for treatment, will be used to derive the hazard ratio (dulaglutide/placebo) and the associated 95% CI. The between-treatment comparison will be based on the p-value from the Cox model. The proportional hazard assumption will be examined graphically. If not met, data will be analyzed using accelerated failure time models. Kaplan-Meier (KM) estimates of the survival curve for each treatment will be generated. The number and proportion of patients with the event will be provided, along with the between-treatment p-value. Tied event times will be handled by the Exact method.

If the number of outcomes is <10, survival analyses will not be performed. Instead, Fisher's exact test will be used and the summary statistics will include the number and proportion of patients with the event plus the between-treatment p-value.

For adjudicated outcomes, the incidence rate per 100 person-years of follow-up will be calculated for each treatment group. The numerator will be the number of patients with the event, and the denominator will be the event-specific total person-years of follow-up divided by 100. Total person-years of follow-up is the sum, over patients, of the time on study until the first outcome (first event time or censoring time). The absolute risk difference (ARD) will then be calculated by subtracting the incidence in the dulaglutide arm from that in the placebo arm. For some analyses, the number needed to treat (NNT) to prevent an additional event will be derived using the incidence rates, that is, $1/(\text{Placebo rate} - \text{dulaglutide rate})$. These analyses will be performed where documented in the SAP, and this statistic will only be derived if the p-value from the Cox model is statistically significant.

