There will be 1 interim analysis and 1 final analysis. The interim analysis will be performed when approximately 61% (730 events) of the positively adjudicated primary endpoint events have occurred. The final analysis will be performed at 100% (approximately 1200) of the positively adjudicated primary endpoint events, if the study is not stopped early. At the interim analysis time point (Figure GBDJ.4.1), superiority will be tested first; if successful, the trial may stop and superiority will be declared. Otherwise, the trial will continue to the end, where, at 1200 events, superiority will be tested followed by noninferiority. The interim and final analyses will be performed on unblinded study data by the Independent Data Monitoring Committee (IDMC) that will use the results and the foregoing decision rules as guidelines. Thus, if the interim analysis shows clear benefit of dulaglutide over placebo for the primary endpoint, the IDMC may recommend early termination of the study. Alternatively, if the boundaries are crossed at the interim analysis, the IDMC may still recommend the trial continue and not stop for early efficacy. At any time during the trial, the IDMC could recommend stopping the trial for safety reasons. The alpha used across the analyses will be monitored by an O'Brien-Fleming spending function (O'Brien and Fleming 1979; Jennison and Turnbull 2000), (for example, with 730 events at the interim, 2-sided alpha = 0.008; power 51.3%). The alpha used at the final analysis will be adjusted to maintain the overall type I error control at a 2-sided significance level of 0.05. This will be accomplished using EAST software to calculate the alpha level for the final analysis considering the actual amount of information at the interim analysis (for example, with 1200 events at the final analysis, 2-sided alpha = 0.048; overall power = 92.8%). At the final analysis, superiority will be tested followed by noninferiority. The adjusted 95% confidence interval (CI) for the hazard ratio will be calculated.

[figure not shown]

Figure GBDJ.4.1. Interim decision rule.

The median unbiased estimator for the hazard ratio will be reported if the trial is stopped early for efficacy at an interim analysis.

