4.1. Determination of Sample Size

For the initial powering of the trial, a minimum of 1067 unique primary endpoint events will be required to provide 90% power to demonstrate the superiority of dulaglutide over placebo at a true hazard ratio of 0.82 and 2-sided significance level of 0.05. To calculate the sample size, the following assumptions were used and yielded a sample size requirement of approximately 9600 patients: (1) two-sided significance level of 0.05; (2) 90% power for the primary endpoint; (3) patient accrual over 3 years; (4) annual placebo group event rate of 2.0% for the primary endpoint; (5) maximum duration of follow-up of 8 years; (6) a detectable hazard ratio of 0.82 between dulaglutide and placebo in terms of the primary endpoint; and (7) annual dropout rate of 0.15%.

The calculations were performed using nQuery Advisor® Version 7.0. This software provides sample size estimates for tests based on exponential survival, accrual period and dropouts. The sample size and other trial characteristics, such as interim analysis power, were also assessed through trial simulation. Trial assumptions were based on information from the scientific leadership of the study and a review of the relevant literature.

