4.3.4.3. Censoring Date

For time-to-event analyses (except for mortality analyses), the censoring date for a patient is the Final Visit date if a Final Visit was conducted, the discontinuation date if the patient discontinues from the study early, or the patient's date of death if the patient dies during the course of the study. This censoring date will be used in all analyses (except the mortality analyses) to censor patients who have not experienced the event of interest.

For time-to-event analyses for mortality, the censoring date for a patient is the Final Visit date if the patient is known to be alive at the time of the Final Visit. If the patient discontinues from the study early, the censoring date will be the last date that the investigator can ascertain the patient was alive.

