4.14.6. Exploratory Analyses: Analyses of Multiple Cardiovascular Events

A patient may experience more than one CV event during the course of the study. For example, a patient may be hospitalized for an unstable angina and later experience a nonfatal MI which

may be followed by death from a CV cause, or a patient may experience 3 nonfatal MIs or 2 nonfatal strokes. In each case, the patients will be considered as having multiple CV events. To assess the effects of dulaglutide on multiple CV events compared to placebo, analyses accounting for multiple CV events will be performed. The analyses will be performed separately for the composite primary endpoint; acute coronary syndrome (ACS) events which include nonfatal MI and hospitalization for unstable angina; MIs; strokes; MACE (composite of nonfatal MI, stroke and CV death) and heart failures requiring hospitalization. In each of these analyses, a patient who experiences multiple events of the endpoint will be considered as having recurrent events of the endpoint. The conditional Gap Time model of Prentice, Williams, and Peterson (PWP-GT) (Prentice et al. 1981) will be used to analyze recurrent CV events. The hazard ratio with 95% CI will be reported for time to the first event, second event, etc. The mean time between successive events will also be reported by treatment group. Baseline characteristics will be compared between groups of patients with no event, only one event, and multiple events (2 or more) regardless of treatment assignment and between treatments within each group. Counts and proportion for categorical variables will be compared using a Chi-square or Fisher's exact test and means for continuous variables will be compared using ANOVA.

4.14.7. Exploratory Analyses: Analysis of Nonfatal Cardiovascular Events with Competing Risk of Death

The composite endpoint of nonfatal CV events (that is, the first occurrence of nonfatal MI, nonfatal stroke, hospitalization for unstable angina, HF requiring hospitalization or an urgent HF visit, or coronary, carotid, or peripheral revascularization), will be analyzed taking into account the competing risk of death. The competing risk model of Fine and Gray will be used (Fine and Gray 1999). Covariates of interest include treatment and the baseline CV risk factors listed in Section 4.13.3.

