4.17.1.1. Analysis of Severe Hypoglycemia

Severe hypoglycemic episodes by patient by visit will be listed using all randomized patients.

The incidence of severe hypoglycemic episodes will be summarized using number and proportion by treatment group and by visit. The overall number and proportion will also be reported as will Kaplan-Meier estimates of the proportion of patients having 1 or more events by treatment group. The number and proportion at each visit are calculated as the number of patients and proportion of patients reporting severe hypoglycemic episodes at that visit. The overall number and proportion are calculated as the total number of patients and proportion of patients reporting severe hypoglycemic episodes during the entire study treatment period. Treatment group comparison will be assessed using a Chi-square or Fisher's exact tests or log-rank tests as appropriate.

Severe hypoglycemia rate per year (number of events per subject per year) will be summarized by yearly visit by treatment group. The rate will be analyzed if enough data points are available. The rate of hypoglycemia will be analyzed using a generalized mixed effect model with a negative binomial distribution (see SAS code below).

```
proc glimmix data=data_glm noitprint empirical initglm method=rspl;
```

```
nloptions maxiter=100 tech=NRRIDG;
class subjid trt visit country stratification variables ;
model count= baseline count country stratification variables trt visit trt*visit/dist=nb
link=log offset=log_days s ddfm=kr;
random visit/subject= subjid type=un residual;
run;
```

An unstructured covariance structure will be used to model the within-patient errors. If this analysis fails to converge, the following covariance structures will be tested in this order: compound symmetry, then, autoregressive. The model will include pooled country, treatment, visit, visit-by-treatment interaction, and baseline. Other covariates of interest, including categorical, continuous and time-dependent may be included.

Time to the first severe hypoglycemia event per patient will also be analyzed via a Cox model described in Section 4.3.4. Incidence rates for 100 person-years will also be presented.

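### Where the SAP uses Kaplan-Meier with deaths censored to estimate the proportion of patients with an event (severe hypoglycemia, glycemic intervention), it will overstate that proportion; the cumulative-incidence ARD for the primary endpoint names no estimator and is open to the same error

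*SAP*

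**What the plan says.** **Censoring.** For every time-to-event analysis other than mortality, SAP 4.3.4.3 censors an event-free patient at the Final Visit, at early discontinuation, "or the patient's date of death if the patient dies during the course of the study". The Statistical Methods part of the Protocol synopsis agrees for analyses in which death is not an outcome of interest.

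**Default output (SAP 4.3.4).** "Kaplan-Meier (KM) estimates of the survival curve for each treatment will be generated". The same section also plans the number and crude proportion of patients with the event, rates per 100 person-years, an ARD from those incidences, and an NNT from the rates.

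**Places where Kaplan-Meier is the stated source of a proportion.** For severe hypoglycemia, SAP 4.17.1.1 plans "Kaplan-Meier estimates of the proportion of patients having 1 or more events by treatment group" (Protocol 12.2.9.2 is parallel). SAP 4.16.1 has matching text for glycemic intervention. Both sections also report the crude number and proportion.

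**Primary endpoint (SAP 4.13.2).** The ARD is to come from the arms' cumulative incidence at the end of the study. No estimator is named, and this is not the rate-based ARD of 4.3.4.

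**Competing death.** One exploratory composite of nonfatal CV events in SAP 4.14.7 "will be analyzed taking into account the competing risk of death", by a Fine and Gray model. No cumulative incidence function is planned for the primary or any individual secondary endpoint.

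**The concern.** Once a patient dies without the event, that patient can no longer have it. Censoring the death and taking 1-KM estimates the risk that would apply if nobody died of other causes. That is not the proportion of randomized patients who have an event, which is how 4.17.1.1 and 4.16.1 label it.

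The primary ARD is exposed for a different reason. Kaplan-Meier is the only estimator of probability over time planned for that endpoint, so a programmer told to compute cumulative incidence may well use it, with non-CV deaths censored. The main absolute measure of benefit would then be slightly too large, and a second ARD defined in 4.3.4 would disagree with it.

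The same caution applies to reading absolute risk off the default curves for any endpoint that leaves out some deaths. What is at stake is the accuracy of stated absolute risks, not the test of the primary hypothesis.

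**Working it through.** **1. The plan's own figures.** The documents state no Kaplan-Meier probability, so I first checked the design figures that carry the event rate.
- Inputs from SAP 4.1: "true hazard ratio of 0.82 and 2-sided significance level of 0.05", and "a minimum of 1067 unique primary endpoint events will be required to provide 90% power". Schoenfeld events = 4(1.960 + 1.2816)² / (ln 0.82)² = 1067.2. This agrees with 1067.
- SAP section 4 gives, for 1200 events, "2-sided alpha = 0.048; overall power = 92.8" percent. A two-look O'Brien-Fleming spending calculation at 730 and 1200 events returns 92.8% at HR 0.82, with interim two-sided alpha 0.0081 as in Protocol 12.2.2.
- With "annual placebo group event rate of 2.0% for the primary endpoint", 3-year accrual, 8-year maximum follow-up and 0.15% dropout per year, 1067 events need 9534 to 9625 patients, depending on how the annual rate is converted to a hazard. The plan says about 9600.

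The 2% rate with constant hazard is therefore a fair basis for what follows.

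**2. Formulas.** Let l be the event rate, m the rate of competing death (assumed equal in both arms) and t the time in years.
- 1-KM with deaths censored: 1 − exp(−l·t)
- Cumulative incidence (what Aalen-Johansen estimates): l/(l+m) × [1 − exp(−(l+m)·t)]

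For small rates the ratio of the first to the second is about 1 + m·t/2. The relative excess then depends mainly on mortality and follow-up, and little on how common the event is.

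**3. Inputs.** l = 0.02 from SAP 4.1. t = 6.5 years, the average follow-up in Protocol 7.1. t = 7.7 years, the longest follow-up implied by 5.6 years minimum (Protocol 7.1) plus 2.1 years of enrollment (Protocol Attachment 5). **m is not in the documents; every value below is an assumption.**

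**4. Primary endpoint, non-CV death competing.**

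| m per year | t (years) | 1-KM | Cumulative incidence | Excess (points) |
|---|---|---|---|---|
| 0.5% | 6.5 | 12.19% | 12.00% | 0.19 |
| 1.0% | 6.5 | 12.19% | 11.81% | 0.38 |
| 3.0% | 6.5 | 12.19% | 11.10% | 1.09 |
| 0.5% | 7.7 | 14.27% | 14.01% | 0.26 |
| 1.0% | 7.7 | 14.27% | 13.75% | 0.52 |
| 1.5% | 7.7 | 14.27% | 13.50% | 0.77 |

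Worked line (m = 1%, t = 6.5): 1 − exp(−0.13) = 0.1219; (0.02/0.03) × [1 − exp(−0.195)] = 0.1181.

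At HR 0.82 and 6.5 years the ARD is 2.08 points by Kaplan-Meier, against 2.05 (m = 0.5%) and 2.02 (m = 1%). The NNT is 48 against 49 and 50. At m = 3% the figures are 1.90 points and 53.

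**5. A rough ceiling for m in the primary endpoint.** CV death is part of the composite, so it cannot exceed 2% per year. Protocol 5.1 says that over two-thirds of deaths in type 2 diabetes are CV. If that held here, non-CV death would be at most half of CV death, about 1% per year. That is a background statement, not a design assumption. It would cap the excess at about 0.4 points at 6.5 years.

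**6. Endpoints that censor all deaths.** The event rates here are also assumed.
- 0.5% per year, 6.5 years: 1-KM is 3.20% against 3.05, 3.00 and 2.91% at mortality of 1.5, 2 and 3% per year, ratios 1.049, 1.066 and 1.100. The approximation gives 1 + 0.02 × 6.5/2 = 1.065 for the middle case.
- 3% per year, 7.7 years: 20.63% against 19.52, 19.17 and 18.83% at 1.5, 2.0 and 2.5% per year, ratios 1.057 to 1.095.

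**7. Simulation.** With 400,000 patients, 2% events, 1% competing death and follow-up of 5.6 to 7.7 years, 1-KM at 6.5 years was 12.20% and Aalen-Johansen 11.81%. Events per 100 person-years came to 2.00, so the rate-based measures recover the true cause-specific rate.

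**The case against.** The strongest objection is that a reader might infer more from 4.3.4 than it says: that event probabilities for every endpoint come from Kaplan-Meier, so that every reported cumulative risk and risk difference is too high. The documents do not support this. The sentence in 4.3.4 plans a curve. The proportion reported there is a crude count over patients, and the ARD and NNT in that section use person-year incidence. None of these is biased by censoring deaths. No section plans a risk difference read from Kaplan-Meier curves, or a comparison of curves across endpoints. This stands, and it limits the point to two named proportions and one unnamed estimator.

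It can also be said that the effect is small and rests on assumed mortality. That stands too. Undetermined deaths count as CV deaths (SAP 4.13), which shrinks the competing pool for the primary endpoint. The 7.7-year figures apply only to the earliest enrollees.

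Finally, the Kaplan-Meier curve for the primary endpoint is specified in the Protocol synopsis and sits naturally beside a Cox model that censors the same deaths. There is no need to remove it. What the objection does not answer is the mismatch in 4.17.1.1 and 4.16.1, where a quantity is labeled a proportion of patients and assigned an estimator that overstates it. The Fine and Gray analysis in 4.14.7 covers neither endpoint.

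**Conclusion.** The point holds in limited form and is minor. The Kaplan-Meier proportions in SAP 4.17.1.1 and 4.16.1 will be too high. With all deaths censored, the relative excess is about 5 to 10% at assumed mortality of 1.5 to 3% per year, for event rates of 0.5 to 3% per year. The documents give no rate for either event; glycemic intervention may be far more frequent than this range, and I have not extended the figures to it.

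The primary ARD in 4.13.2 is affected only if Kaplan-Meier is used for it, and then by little: 0.2 to 0.4 points on a 12.2% risk at 6.5 years, with non-CV death of 0.5 to 1% per year. Its conflict with 4.3.4 needs resolving in any case. Hazard ratios, p-values, alpha, power and the event count do not change. The sizes assume constant hazards and the same competing mortality in both arms.

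**What to change.** - **SAP 4.17.1.1 and 4.16.1:** replace the Kaplan-Meier proportion with the Aalen-Johansen cumulative incidence, with death as the competing event. Keep the crude counts and the planned tests.
- **SAP 4.13.2:** state that the cumulative-incidence ARD uses Aalen-Johansen with non-CV death competing, at a named time point. Reconcile it with 4.3.4 so that one ARD is primary and any other is labeled as rate-based.
- **SAP 4.3.4:** add Aalen-Johansen curves for endpoints that omit some deaths.
- **Keep** the Cox model and its p-value, and the Kaplan-Meier curve that the Protocol specifies for the primary endpoint.

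The cost is a few SAP sentences and one more procedure option, using dates of event and death already collected. Stated absolute risks become slightly smaller. Protocol 12.2.1 lets such a change be made and justified in the SAP, so the parallel text in Protocol 12.2.9.2 should not need an amendment.

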4.3.4.1. Time to Event

For each patient, time-to-event for an event of interest will be the number of days between the date of randomization and the onset date of the event plus 1 day if the patient experiences the event or the number of days between the date of randomization and the censoring date (Section 4.3.4.3) plus 1 day if the patient does not experience the event. If a patient experiences

multiple events (for example, multiple strokes) the date of the first event will be used, unless otherwise specified.

4.3.4.2. Person-Years of Follow-up

Person-years of follow up for an event of interest will be calculated for each patient as the time to event (defined in Section 4.3.4.1) divided by 365.25.

The total person-years of study follow-up will be calculated for each patient as the number of days between the randomization date and the censoring date plus 1 day divided by 365.25. The censoring date is defined in Section 4.3.4.3 for time-to-event analyses (other than mortality analysis).

4.3.4.3. Censoring Date

For time-to-event analyses (except for mortality analyses), the censoring date for a patient is the Final Visit date if a Final Visit was conducted, the discontinuation date if the patient discontinues from the study early, or the patient's date of death if the patient dies during the course of the study. This censoring date will be used in all analyses (except the mortality analyses) to censor patients who have not experienced the event of interest.

For time-to-event analyses for mortality, the censoring date for a patient is the Final Visit date if the patient is known to be alive at the time of the Final Visit. If the patient discontinues from the study early, the censoring date will be the last date that the investigator can ascertain the patient was alive.

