**Statistical Methods:**

The primary efficacy measure is the time to first occurrence of the composite endpoint of death due to CV causes, nonfatal MI, or nonfatal stroke (adjudicated as such). The primary analyses will be based on the intent-to-treat principle and will use time-to-event analyses via a Cox proportional hazards regression model. Estimates of hazard ratios and 95% confidence intervals will be calculated and treatment group comparisons will be based on the p-value from the Cox model. Dulaglutide will be considered different from placebo if the 2-sided p-value from the primary analysis (adjusted for interim looks) is  $<0.05$ . Kaplan-Meier estimates of the survival curve for each treatment will be generated. The incidence rate per 100 person-years of follow-up will be calculated for each treatment group.

Analyses of the secondary efficacy and select additional measures will be based on the time from randomization to the occurrence of the first event, with patients analyzed in the treatment group to which they were randomized (according to the intent-to-treat principle). Where applicable, analyses will be based upon adjudicated events. Patients who complete the study but do not experience an outcome will be censored on the last day of their follow-up. Patients who discontinue from the study will be censored on their discontinuation dates or their last contact dates, whichever is later. Patients who die during the study will be censored as of the date of death for all time-to-event analyses where death is not an outcome of interest. Patients who prematurely discontinue assigned treatment will be followed until the end of the study.

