4.3.4.4. Handling of Missing Dates

For all adjudicated events, the date the Clinical Endpoints Committee (CEC) indicates the event occurred will be used in all analyses. If this date is missing then the investigator-reported date will be used.

For an incomplete endpoint event (that is, primary endpoint or secondary efficacy endpoint events) date, imputation will be performed as outlined below:

- If only the day of the event date is missing, the day will be imputed as the 15th of the reported month.
- If both the month and day of the event date are missing, the month and day will be imputed as 30 June of the reported year.
- If only the month is missing, the month will be imputed as June.
- In the case that the imputed event date falls after the patient's censoring date as defined above, the incomplete event date will be imputed as the censoring date (for example, if an incomplete onset date of an event is X-X-2012 and the patient's censoring date is 05-22-2012, then the onset date of the event will be imputed as 05-22-2012 rather than as the date of 06-30-2012 as imputed by following the procedure stated above for missing month and day).

For an incomplete death date, imputation will be performed as described below:

- If only the day of the death date is missing, the day will be imputed as follows.
 - (a) If the date of the last reported contact for the patient falls in the same month and year as the death date where the day is missing, the day will be imputed to fall halfway between the last reported contact and the end of the given month (for example, if an incomplete death date is 04-X-2012, and the date of the last reported contact is 04-22-2012, the death date will be imputed as 04-26-2012);
 - (b) If the date of the last reported contact for the patient occurs before the reported month and year of the death date, the day will be imputed as the 15th of the reported month (for example, if an incomplete death date is 04-X-2012, and the date of the last reported contact is 03-26-2012, the death date will be imputed as 04-15-2012).
- If both the month and day of the death date are missing, the month and day will be imputed as follows.

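### The SAP stops event-free follow-up at study discontinuation but puts no such limit on events, and this departs without explanation from the protocol's censoring rule

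*SAP*

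**What the plan says.** SAP 4.3.4.3 sets the censoring date for all non-mortality analyses at the Final Visit, at death, or at "the discontinuation date if the patient discontinues from the study early". It limits the use of that date to patients without the event: "This censoring date will be used in all analyses (except the mortality analyses) to censor patients who have not experienced the event of interest".

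SAP 4.3.4 says of events: "For each analysis, all adjudicated events in the locked database will be used". SAP 4.3.4.1 times an event by "the onset date of the event plus 1 day if the patient experiences the event" and sets no upper limit. The only cap is in SAP 4.3.4.4. It begins "In the case that the imputed event date falls after the patient's censoring date as defined above", so it covers incomplete dates that are imputed, not known ones.

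For mortality analyses the SAP extends follow-up of early discontinuers: "the censoring date will be the last date that the investigator can ascertain the patient was alive".

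The protocol synopsis, under Statistical Methods, has a different rule: "Patients who discontinue from the study will be censored on their discontinuation dates or their last contact dates, whichever is later". The paragraph containing it opens "Analyses of the secondary efficacy and select additional measures will be based on the time from randomization to the occurrence of the first event".

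**The concern.** Follow-up that depends on the outcome is a recognised source of bias. If post-withdrawal time is kept for patients who turn out to have had an event and discarded for those who did not, event rates are pushed up in both arms. They are pushed up more in the arm with more withdrawals, so the hazard ratio moves when study withdrawal is unequal.

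Information after withdrawal is expected. Protocol 7.1.5 and 8.3.3 ask sites to use family, physicians and national registers or death indices.

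Three further gaps affect the primary dataset:

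- The SAP does not say which of its two censoring rules governs the primary composite. Read literally, the non-mortality rule applies.
- SAP 4.3.4.3 gives no date for a patient lost to follow-up who has no Final Visit, recorded discontinuation or death. SAP 4.13.5 treats lost patients as a separate group and uses their last contact date.
- Protocol 12.2.1 calls for changes to analysis methods to be described and justified in the SAP and/or the study report. The SAP revision history mentions no change to censoring.

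**Working it through.** **1. The rules applied to two patients (illustration).** Both withdraw at year 3, and a check at year 5 returns information on both. Patient A had an MI at year 4.5: the SAP counts an event at 4.5. Patient B had no event: the SAP censors at 3. Under the protocol's rule, taking the check as last contact, B would contribute 5 years.

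**2. Design figures.** The disputed section states no figure, so this checks only the design. Events for 90% power at HR 0.82, two-sided 0.05: 4(1.960 + 1.282)² / (ln 0.82)² = 42.03 / 0.03938 = 1067.2, rounded up to 1068, against 1067 in SAP 4.1. Power with 1067 events is 89.99%. The overall power of 92.8% at 1200 events also reproduces.

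**3. Inputs.** From the documents: 9600 patients randomised 1:1, placebo event rate 2% a year, dropout 0.15% a year, minimum follow-up 5.6 years, enrolment over 2.1 years (so a maximum of 5.6 + 2.1 = 7.7). Assumed: exponential times, follow-up u uniform from 5.6 to 7.7 years, true HR 0.85 (dulaglutide rate 1.7%), and post-withdrawal follow-up running to study end. The last makes the counts upper bounds.

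**4. Formulas.** With event hazard λ, withdrawal hazard δ and n patients, averaged over u:

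- events before withdrawal: B = n·λ/(λ+δ)·(1 − e^(−(λ+δ)u))
- events after withdrawal: L = n·(1 − e^(−λu)) − B
- person-years to event or withdrawal: T = n·(1 − e^(−(λ+δ)u))/(λ+δ)
- crude rate under the literal SAP rule, with a fraction q of late events found: (B + qL)/T

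**5. Size at equal withdrawal** (2% event rate in all 9600 patients, q = 1):

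| Withdrawal per year | Withdraw before event | Person-years that differ | Late events | Rate per 100 PY (true 2.00) |
|---|---|---|---|---|
| 0.15% | 89 | 293 | 5.9 | 2.01 |
| 0.5% | 294 | 968 | 19 | 2.03 |
| 1% | 578 | 1914 | 38 | 2.07 |

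With the dulaglutide rate at 1.7%, late events at 0.15% are 2.9 + 2.5 = 5.4.

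**6. Rate ratio, true value 0.85:**

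| Placebo vs dulaglutide withdrawal per year | 25% of late events found | All found |
|---|---|---|
| equal (0.15%, 0.5% or 1%) | 0.850 | 0.850 |
| 0.15% vs 0.30% | 0.851 | 0.854 |
| 0.5% vs 1% | 0.854 | 0.864 |
| 1% vs 2% | 0.857 | 0.878 |

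Worked line for 0.5% vs 1%, 4800 per arm, all found:

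- placebo: (587.8 + 9.7)/29,389 = 2.033 per 100 PY
- dulaglutide: (496.4 + 16.5)/29,199 = 1.757 per 100 PY
- ratio: 0.864

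T omits the time that late-event patients accrue between withdrawal and event. Adding it (21.6 and 37.0 PY) gives 597.5/29,411 = 2.031 and 512.9/29,236 = 1.754, ratio 0.8636, so the table overstates slightly. A simulation with Cox models (placebo hazard 1.95% a year, 200 replicates) gave shifts of the same size: 0.852 to 0.866 at 0.5% vs 1%, and 0.850 to 0.878 at 1% vs 2%.

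**The case against.** The strongest case is that this is a wording difference with no practical effect. The plan expects 0.15% dropout a year and 9500 completers of 9600, where nothing moves. The larger shifts need dropout several times the plan, a 2:1 imbalance and full discovery of later events. Registers mainly reveal deaths, and a nonfatal MI or stroke also needs source documents for adjudication. The two extreme missing-data analyses in SAP 4.13.5 include one far harsher than this effect. The synopsis sentence sits in a paragraph about secondary and select additional measures, protocol 12.2.1 allows changes to be explained in the study report, and the SAP history lists only key changes.

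Much of this stands. The size at plan is negligible, and the protocol's reach to the primary endpoint is the natural reading but not an explicit one. But the SAP applies its own rule to those secondary measures too, so the conflict remains. The SAP 4.13.5 analyses bound missing outcomes without repairing the main rule. The per-protocol and site-stratified analyses in SAP 4.13.4 do not test it either.

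Two stronger readings are tempting but unsupported:

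- A reader might infer that a late CV death could count as CV death yet not in the composite. That requires dropping events after the censoring date, which is the opposite of the reading that creates the asymmetry. Under the literal text the event counts in both.
- A reader might expect more withdrawal on dulaglutide because of gastrointestinal effects. Those would mainly lead patients to stop study drug. Protocol 7.1.4 and 8.3.3 keep such patients in the study, and the SAP date concerns leaving the study. No section predicts unequal study withdrawal.

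**Conclusion.** The concern holds as a defect in the rule. As written, the SAP makes post-withdrawal follow-up depend on outcome, differs from the protocol without saying why, and leaves open the rule for the primary composite and for patients lost to follow-up. The two rules coincide only if last contact never falls after the discontinuation date, a date that the SAP does not define.

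At the planned dropout in both arms the hazard ratio moves by less than 0.001, and equal withdrawal at any rate examined leaves it at 0.850. The values 0.864 and 0.878 rest on assumed unequal withdrawal and full discovery of later events; with 25% discovery they are 0.854 and 0.857. They are not forecasts. With more withdrawal on dulaglutide the shift is towards 1, so these scenarios do not suggest a false claim of superiority. The reason to act is that the primary endpoint's censoring should be unambiguous before unblinding.

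**What to change.** Set one end-of-follow-up date per patient for MACE and its components: the Final Visit, death, or, for early discontinuers and patients lost to follow-up, the later of discontinuation and last contact.

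- Use that date both to censor and as the cut-off for counting events, and amend SAP 4.3.4 and 4.3.4.1 to match.
- State that MACE follows this rule.
- Define last contact identically whether or not an event was found, including dated negative register, family or physician checks where available. Without dated negative checks, an event found later would extend follow-up and a clean check would not, so the asymmetry would return.
- Report events found after the cut-off in a sensitivity analysis.
- If the sponsor prefers the SAP's discontinuation date, record and justify the departure from the protocol and apply the same cut-off to events.

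The cost is SAP wording and one derived date. The documents do not say whether negative checks are dated; where they are not, the rule has to rest on the contacts that are recorded.
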